### **Brief Summary and Description**

The purpose of this study is to conduct a pilot study as part of a Career Development Award (K23) funded through NIH. We will recruit overweight or obese (OB) cigarette smokers ( $BMI \geq 25$ ) to participate in 8 weeks of either a self-regulation weight gain prevention intervention (SR; an intervention based on self-regulation approaches to produce and maintain weight loss shown to be effective for weight gain prevention) or lifestyle education (LE; attention-placebo control) followed by 8 weeks of smoking cessation treatment. We will conduct a small RCT with 60 OB smokers comparing SR to LE, with both conditions subsequently receiving smoking cessation counseling and combination nicotine replacement therapy to assess intervention feasibility and acceptability and obtain preliminary effect size data. Up to 60 OB smokers from the community will participate in 8 weeks of group weight gain prevention (self-regulation plus large changes in behavior) or lifestyle education (attention-placebo control) followed by 8 weeks of group smoking cessation treatment with nicotine replacement therapy as part of an RCT. Assessments will occur at baseline, week 9 (quit day), 1 month post-quit, 2 months post quit, and 3 months post-quit.

### **Specific Aims**

We aim to conduct a small RCT with 60 OB smokers comparing SR to LE, with both conditions subsequently receiving smoking cessation counseling and combination nicotine replacement therapy to assess intervention feasibility and acceptability and obtain preliminary effect size data regarding the following hypotheses: Smokers in the SR vs. LE condition will have better biochemically verified point-prevalence abstinence from smoking at the end of smoking cessation treatment and at follow-ups, with a medium effect size. Smokers in the SR vs. LE condition will have less weight gain at the end of smoking cessation treatment and at follow-ups, with a medium effect size.

We will also examine potential mechanisms of action for efficacy of SR on improved smoking outcomes, expecting that: Smokers in the SR vs. LE condition will have greater increases in self-efficacy for managing weight and for quitting smoking and greater decreases in negative affect and delay discounting prior to quitting. Self-efficacy, negative affect, and delay discounting will be associated with abstinence at follow-ups.

### **Methodology**

#### **Project Purpose**

This project focuses on collecting pilot data to inform a larger clinical trial for preventing weight gain and improving smoking cessation outcomes in overweight and obese smokers who are disproportionately at risk for disease, disability, and premature death but may be reluctant to give up smoking due to the fear of subsequent weight gain and trouble managing their weight without cigarettes. Helping these individuals lose weight prior to quitting smoking could provide a buffer against post-cessation weight gain and may improve mood, help increase the salience of future health outcomes, and increase self-efficacy for tackling the challenges associated with quitting smoking. Use of a multiple health behavior change intervention can maximize anticipated health benefits of smoking cessation and reduce the potential for relapse to smoking due to post-cessation weight gain. With an effective program, more overweight or obese smokers may be willing to attempt smoking cessation which could impact the two leading causes of preventable mortality in the US.

## **Project Description**

Overweight and obese smokers who want to quit smoking and minimize weight gain will be assigned to one of two experimental conditions before entering smoking cessation counseling in a between-groups design in order to determine study feasibility and provide preliminary data on change in weight and abstinence from smoking. Participants will be assigned to either weight gain prevention (self-regulation plus large changes in behavior) or lifestyle education (attention-placebo control) for 8 weeks. Afterward, both groups will participate in 8 weeks of smoking cessation with combination NRT (transdermal patch and lozenges). Participants will begin using lozenges at week 6 (pre-quit). Both groups will participate in 8 weeks of smoking cessation with combination NRT (transdermal patch and lozenges) starting at week 9. Treatment will begin once the identified number of participants to form a group has been recruited.

Assessments will occur at baseline, at week 9, and 1, 2, and 3 months after the target quit date.

## **Participant Population**

Inclusion/exclusion criteria. The participants will be adult men and women 18-75 years old.

### Inclusionary criteria are:

- a) BMI 25 kg/m^2
- b) smoked  $\geq$  5 cigarettes/day during the past year
- c) self-reported motivation to quit smoking
- d) self-reported desire to prevent or minimize weight gain during smoking cessation
- e) ability to understand informed consent
- f) access to a smart phone or tablet

### Exclusionary criteria are:

- a) current smoking cessation or weight loss treatment/medication
- b) more than 1 day/week use of tobacco or nicotine from sources other than cigarettes (other than non-daily use of e-cigarettes in addition to combustible cigarettes)
- c) weight loss of 20 lbs or more within the past 6 months
- d) self-reported diagnosis or treatment for an alcohol or substance use disorder within the past 6 months (with the exception of maintenance therapies)
- e) endorsing recent symptomology suggestive of an eating disorder, an alcohol or substance use disorder, severe depression, or suicidal ideation
- f) self-reported diagnosis or treatment or evidence of an eating disorder or severe psychiatric disorder (e.g., schizophrenia or bipolar disorder)
- g) not stabilized on psychotropic medications
- h) current use of medications known to interact with smoking cessation
- i) clinically significant medical condition.

Physicians of individuals with type 2 diabetes or controlled hypertension will approve study participation of interested individuals and will attest that they will be responsible for any medication adjustments that are needed.

## **Procedures**

OB smokers (n=60) will be randomized to either a combined self-regulation plus large changes (SR) intervention in advance of smoking cessation treatment condition (n=30) or to a healthy lifestyle education (LE) in advance of smoking cessation treatment attention-placebo control condition (n=30) for 16 weeks. The study will include up to 18 groups each run in succession with approximately 4-6 participants recruited for each group in order to have 3-5 participants beginning each group. Groups will be randomly assigned to one of the two treatment conditions using a random number generator after participants have completed all pretreatment assessments. Participants will learn their condition assignment at the first treatment session. Feasibility and acceptability will be monitored. Assessment of smoking/abstinence and weight will be obtained at baseline, on Quit Day, and 1, 2, & 3-months post-quit.

Recruitment procedures- Participants will be recruited through print and electronic advertising (e.g., newspaper, magazine, listserv, websites, online ads), advertisements on buses or at bus stops, and via community outreach (e.g., providing study information and pamphlets to local physicians).

Initial screening: Interested individuals will be given several options for contacting the study and for completing initial eligibility screening depending on advertising modality (e.g., call the study telephone number, email the study email address, provide their contact information in an electronic interest form). Individuals will be given the option of either completing initial screening using an online screener or being contacted by study staff for telephone screening.

Phone screening: Individuals who are screened over the telephone will be contacted by study staff. They will be provided with a brief description of the study, and will be asked if they are interested in participating. Verbal consent will be obtained prior to the potential participant's completion of the phone screen using a bulleted consent form that includes key information. Individuals who indicate that they would like a copy of the consent document will be provided a copy via email.

Online screening: Online screening will be conducted using Brown's Qualtrics survey software. Individuals who are screened using an online screener will be provided with the same brief description of the study used in the phone screening. They will then review verbal consent information (bulleted points reviewed via telephone) and agree to be screened. Individuals who indicate that they would like a copy of the consent document will be able to download a copy. Those who agree to participate will be redirected to a screening questionnaire. Individuals who complete the online screener will be contacted via phone or email to provide any necessary clarifications to their screening questions and proceed to the next step of enrollment if eligible.

Online orientation session: Those who are deemed eligible on initial screening and interested will be scheduled for a brief study orientation and information session. This session will occur using the video conferencing platform Zoom. During the orientation session, the study will be described. Participants will be asked to generate pros of cons of participating using the Methods-Motivational Interviewing (MMI) approach. The MMI method has been used to improve study retention by helping participants consider pros and cons of participating prior to enrolling in a research study.

Screening, consent and enrollment, and baseline assessment: Individuals who complete the orientation session and remain interested in participating will be offered the opportunity to be scheduled for a full baseline assessment remotely using Zoom. Electronic informed consent will be obtained after the potential risks and benefits of participation are explained. Participants will be asked to provide the names of at least two family members or friends who could help us locate them at follow-up if we are unable to reach them. After informed consent, full screening will occur followed by baseline assessments for those who are eligible.

Interventions- The treatment will consist of 16 weekly, 60-minute, group sessions that will take place remotely using Zoom. The treatment will consist of 16, manualized, weekly sessions. The first 8 sessions will focus primarily on SR or LE (sessions 1-8) according to assigned condition with Quit Day preparations incorporated into weeks 7 & 8. The second 8 sessions (sessions 9-16) will focus primarily on smoking cessation and will also include brief discussions of weight and review of previously covered SR and LE topics according to assigned condition. Participants will be sent session handouts, a scale, and other intervention materials such as nicotine replacement therapy. In rare or extenuating circumstances, if a participant needs study materials in a time-sensitive way, they may be offered the opportunity to purchase these materials and be reimbursed via a ClinCard. The treatment groups will be led by study interventionists. All interventionists will be trained to provide treatment in both arms of the study. Study

interventionists will be postdoctoral fellows, clinical/counseling graduate students, or hired staff with backgrounds in clinical/counseling psychology, social work, nutrition, or another related field with intervention experience. Interventionists will be under the supervision of PI, a licensed clinical psychologist, with guidance from mentors as needed. Based on interventionist availability, if needed, the PI may also serve as an interventionist.

Self-regulation plus large changes in behavior (SR). The active intervention is based on self-regulation theory and is similar to interventions tested previously and shown to be effective in reducing weight gain and weight regain. The initial 8-week program will include weekly group sessions focused on teaching self-regulation and efforts to produce a 10 lb weight loss to buffer against anticipated post-cessation weight gain based on the SR approach. The key concepts of the intervention: Self-Regulation. Participants will be taught the core self-regulation skills for controlling their weight: a) weighing themselves daily; b) detecting small changes in weight as soon as they occur; c) implementing problem-solving skills and learned strategies to combat changes in weight; d) evaluating the success of strategies implemented; e) rewarding themselves for successful weight loss and weight maintenance or f) making behavioral changes if weight gain occurs. These strategies are introduced over the course of the 8 weeks, with the initial weeks stressing the importance of daily self-weighing and learning to use the scale for information (rather than self-evaluation). At the end of the initial 8 weeks, the participants will be introduced to a color-coded system to help them accomplish steps b-f of the self-regulation model. The goal for the first 8 weeks of the program will be to lose 10 lbs in order to buffer against expected weight gain. To accomplish this, participants will be given a reduced calorie goal (1200-1500 kcal/day if <200 lbs or 1500-1800 kcal/day if >200 lbs). They will be instructed to self-monitor their intake and taught strategies for reducing caloric intake (e.g. reducing fat content of foods) and strategies for dealing with high-risk situations such as eating out. Structured physical activity, which is activity similar in intensity to brisk walking that lasts at least 10 minutes, will also be prescribed and self-monitored, starting with a goal of 50 minutes per week (10 minutes per day on 5 days per week) and gradually increasing to 150 minutes per week.

Weeks 9-16 will focus on smoking cessation, but each session will include a private weigh-in and brief group discussion of strategies to maintain weight loss and prevent post-cessation weight gain. To maintain the weight losses achieved thus far and prevent post-cessation weight gain, participants will be taught to use a color zone system (Red, Yellow, Green) for weight maintenance to guide their behavior after completing the initial 8-week weight control program. The weight goals used to define the zones will be individually tailored based on the initial weight changes. Participants will be encouraged to weigh themselves daily and at the end of each week and to assess their current weight relative to their individual color zones. If participants are in Green, they will be encouraged to reinforce their success (with a sticker or small amount of money); if they are in Yellow they will be taught to begin monitoring their behavior more carefully and identify area to make changes to get back on track; if they are in Red, they will be encouraged to return to full self-monitoring of intake and activity and resume their original calorie intake and goals. During smoking cessation, the goal will be to minimize weight gain for those who achieved targeted weight loss as well as for those who did not. This Red, Yellow, Green system for weight maintenance has had demonstrable success in prior studies of the self-regulation model.

Healthy lifestyle education attention-placebo control (LE). Participants in this group will be provided with information on the obesity epidemic and the importance of a healthy lifestyle to use at their own pace as they wish. They will receive basic education about principles of healthy eating (e.g., simple vs. complex carbohydrates) and physical activity during the first 8 sessions. During sessions 9-16, the focus will be on smoking cessation. Sessions will also include lifestyle education information such as why weight gain occurs after smoking cessation. This group will not be taught any specific behavioral self-regulation skills to help them change their behaviors. Providing basic education about diet and exercise has produced minimal weight loss in other clinical trials.

Counseling for smoking cessation. A combination of behavioral treatment and medication is recommended according to clinical practice guidelines. Treatment elements associated with greater odds of success such as support and problem-solving skills will be incorporated throughout the counseling. Participants will be introduced to smoking cessation counseling beginning at week 7. While weeks 7 & 8 remain predominantly focused on creating a weight loss buffer (SR) or learning healthy lifestyle information (LE), approximately 20 minutes of each of these sessions will be dedicated to preparing participants to quit smoking. This will include providing basic information about smoking and successful quitting (e.g., the addictive nature of smoking, the fact that smoking even a puff increases the likelihood of relapse, typical symptoms and duration of withdrawal, benefits of quitting, importance of removing cigarettes from the environment) and encouraging participants in their quit attempts. Participants will be asked to determine a plan for high-risk situations and will be taught behavioral self-management strategies (i.e., avoid, alter, alternative), and cognitive coping strategies such as using self-statements (e.g., benefits of quitting, statements of determination). Participants will be instructed to start using NRT lozenges beginning at week 6 (pre-quit). They will begin using combination NRT (patch + lozenge) on the morning of their Quit Day which coincides with their 9th treatment session (NRT procedures below). Post-quit sessions (weeks 9-16) will focus on reinforcing success, providing encouragement, coping with cravings, discussing reactions to quitting and to NRT, problem solving, dealing with slips, planning for high-risk situations, encouraging the use of social support, and noting benefits of quitting. A brief portion of each smoking cessation session will include continued discussion of self-regulatory weight gain prevention or healthy lifestyle education information. If conducted remotely, participants may be mailed a device to monitor their CO.

The smoking intervention will also include a texting component to provide additional support to participants as they prepare to quit smoking and during smoking cessation (study weeks 8-16). This intervention will be administered by LiveInspired, a company with extensive experience in providing text messaging services, using TextMyQuit (TMQ). Participants will receive on-demand support and encouragement by texting “crave” or “slip”.

NRT procedures. NRT will be mailed to participants. Participants will be counseled on the proper use of NRT before initiating use with ample opportunity to ask questions and written materials (e.g., how to use it, precautions for use, possible side effects, storage information, what to do if a dose is missed or certain unwanted symptoms occur).

Participants will receive 3 weeks of pre-quit, preparation-phase, nicotine mini-lozenges dosed per mini-lozenge labeling (smoke within 30 min of waking, 4 mg; smoke more than 30 min after waking, 2 mg). Participants will be instructed to use one mini-lozenge every 1-2 h and up to 12 daily, with a goal of using at least 5 daily. Participants will be advised to try to reduce their smoking, reduce the range of contexts in which they smoked, and substitute mini-lozenges for cigarettes during the preparation phase consistent with past research (e.g., Piper et al., 2018).

Beginning on their target Quit Day, participants will be encouraged to use an average of 9 mini-lozenges/day, unless they experienced negative side effects (as described in informed consent and during treatment). Participants will be encouraged to taper their mini-lozenge use to zero over weeks 6-8.

Participants will receive 8 weeks of nicotine patch starting on their target quit day (participants who smoke >10 cigarettes/day: 4 weeks of 21 mg, 2 weeks of 14 mg, and 2 weeks of 7 mg nicotine patches; participants who smoke ≤10 cigarettes/day: 6 weeks of 14 mg, and 2 weeks of 7 mg nicotine patches). Use and side effects of NRT will be queried weekly post-quit.

Ensuring integrity of counseling. Sessions will be audio recorded to ensure fidelity to manualized session content as discussed with participants during informed consent procedures. PI will hold supervision

meetings with the interventionists following review of audio from the sessions. Feedback will be given to interventionists to keep delivery consistent and prevent drift, and ensure that treatment is delivered competently (e.g., appropriate flexibility, understanding of the participant, empathy).

Assessment. All assessments will be conducted by research assistants blind to intervention condition. Participants will be compensated \$30 for the baseline screening session, \$35 for their assessment on Quit Day, and \$40, \$45, and \$50 for the 1, 2, and 3-months post-quit assessments, respectively. Participants will receive a completion bonus of \$10 for completing each post-Quit Day assessment within 2 weeks of the specified date (up to \$30). Schedule of assessment by time point is included in Table 1. Participants can choose to be paid via a ClinCard (mailed to the participant) or using an Amazon electronic gift card (sent electronically via email).

Initial screening: Age, height, weight, number of cigarettes per day, days of other tobacco products in last month, current use of any smoking cessation method, current use of other nicotine or tobacco products, access to a smart device, current addiction treatment, screening for selected medical and psychiatric problems, changes in psychiatric medications, recent or planned pregnancy or nursing, recent dieting and weight loss or weight gain, and degree of desire to quit smoking and to minimize weight gain, both assessed using Likert scales (0 = not at all, 10 = extremely).

Screening at baseline: 1. Height and weight to calculate BMI. 2. Screening interview- Age, number of cigarettes per day for past year, use other nicotine or tobacco products, current smoking cessation or weight loss treatment/medication. 3. Medical conditions and medications screening tool will be used to screen for recent medical, substance-related, or psychiatric hospitalizations and any medical conditions or medications that warrant exclusion for safety (determined by PI and study Medical Monitor). 4. Participants will complete questionnaires to assess for symptoms of disordered eating (Eating Disorders Assessment (EDA), severe depression or suicidality (total score  $\geq 20$  or question 9 score  $\geq 1$  on the Patient Health Questionnaire 9-item depression index (PHQ-9), reviewed by clinician), or substance or alcohol use disorders (CAGE-AID score  $\geq 2$ , reflecting past 6 months). 5. Salivary cotinine and/or exhaled carbon monoxide (CO) to confirm smoking status.

Feasibility. In order to quantify feasibility of recruitment and enrollment during pilot testing the number of participants screened and enrolled will be documented per month during periods of active recruitment. The proportion of enrolled participants completing planned assessment sessions will be calculated.

Acceptability. Treatment attendance- Attendance at all counseling sessions will be recorded. Percentage of participants completing each treatment session will be calculated to examine treatment-specific retention rates. Participant Feedback- Participants will complete brief assessments at weeks 9 & the end of treatment (month 2) to assess: 1) helpfulness of interventionist, 2) perceived clinical usefulness, 3) personal relevance, 4) level of engagement, and 5) overall satisfaction scored 1 (not at all) to 5 (extremely) on a Likert-scale. Data on acceptability of other aspects of intervention (e.g., group component, pre-quit NRT, nicotine patches, nicotine lozenges, and smoking text messages) will also be assessed using a 5-point Likert scale. Participants will also be asked to provide brief feedback on sessions after each session.

Patient adherence. Physical activity will be assessed using the Paffenbarger Activity Questionnaire (PAQ). Diet will be assessed using a questionnaire assessing frequency of eating behaviors (consuming sugar sweetened beverages, eating fast food) with measurable changes following the use of self-regulation strategies associated with weight outcomes. NRT use. Utilization of NRT will be assessed post-quit through weekly self-report using calendars. Utilization of a fitness app (SR condition only) will be recorded (e.g., number of days for which any dietary tracking occurred) during the weight management portion of the intervention (weeks 1-8).

Intervention outcome effects. Weight: Participants will be weighed in street clothes, without shoes. Weight will be measured at baseline, Quit Day, and post-quit follow-up sessions via an electronic scale. Timeline Follow-Back (TLFB): During each post-quit assessment, participants will be asked to report on smoking since the last assessment. Seven-day point prevalence abstinence will be based on self-report (7 consecutive days of no smoking) and biochemical verification. Exhaled Carbon Monoxide (CO): Alveolar CO will be assessed via the iCOquit® Smokerlyzer® CO  $\leq$  6 ppm, to verify self-reported abstinence on Quit Day and at post-quit follow-up sessions.

Process measures. These measures of theoretical processes will be collected at baseline and week 9 to explore effects of treatment on putative mechanisms and subsequent outcome variables. Self-efficacy. Smoking Self-Efficacy Questionnaire (SEQ-12): has two six-item subscales that measure confidence in ability to refrain from smoking when facing internal stimuli (e.g., feeling depressed) and external stimuli (e.g., being with smokers). Weight-efficacy after quitting smoking (WEAQ): is a six-item scale that assesses confidence to prevent weight gain after quitting smoking. Mood. The Positive and Negative Affective Schedule (PANAS): is a 20-item mood inventory with two scales that assess positive and negative affective states. Delay Discounting. Monetary Choice Questionnaire (MCQ): is a 27-item questionnaire that assesses preferences for either a smaller, immediate reward or a larger, delayed reward in order to calculate how quickly a reward diminishes in value as a function of its delayed receipt.

Other measures of interest. Substance use. The timeline followback (TFB) method of assessment to collect data on use of marijuana and other substances. Other measures include: (Modified) Weight Bias Internalization Scale (WBIS), Internalized Stigma of Smoking Inventory (ISSI), Perceptions of Smoking-Related Stigma Scale (PSRSS), Brief Wisconsin Inventory of Smoking Dependence Motives (B-WISDM), Subjective Social Status Ladder (SSS Ladder), Everyday Discrimination Scale (EDS), Brief Self-Control Survey (BSCS), Paffenbarger (Physical Activity) Questionnaire, Self-Weighing Behavior, Eating Away from Home Questionnaire, Health Changes Questionnaire. Utilization of text-based support for quitting will be assessed by determining the number of participants who text “crave” or “slip” and the number of times an individual sends a message with either phrase.

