#### Data Analysis Plan

Feasibility & Acceptability. Average monthly number of individuals screened and enrolled will show feasibility of screening and recruitment. The proportion of participants completing the final study assessment will show feasibility of retention. Response to SR & LE conditions. Attendance. The percentage of treatment sessions attended through week 10 (one week post-quit) will be calculated and compared between conditions; average attendance of  $\geq$  70% in both arms suggests good acceptability. Participant Feedback. Participant ratings of intervention satisfaction mean scores  $\geq$  3.5 (5-point scale) shows acceptability in each condition.

Intervention effects on treatment outcome variables: Based on ITT principles, all assigned participants will be used in analyses regardless of adherence and missing data. Participants with missing data will be assumed to have smoked and to have regained 0.3 kg/month (positive imputation) and analyses will be repeated using multiple imputation for sensitivity analyses. Generalized estimating equations (GEE) Group x Time analyses will be used for weight change and abstinence. Abstinence. The dependent variable of 7-day point-prevalence abstinence will be analyzed by time (Quit Day, 1, 2, 3-months post-quit) and conditions. Weight. The dependent variable of weight, will be analyzed by time (baseline, Quit Day, 1, 2, 3- months post-quit) and conditions. Secondary exploratory analyses will repeat the GEE analyses adding sex as a variable, and (separately) adding any/no weight loss at week 9 as a variable in predicting smoking abstinence.

Putative mechanisms will be examined using regression analyses to test the effects of treatment on proposed mechanistic variables at week 9, controlling for baseline values. Regression analyses will also test the effects of these proposed mechanisms on follow-up smoking outcomes. Notably, detection of statistically significant effects is not an objective in this limited-powered study.

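### Treatment groups are randomised and treated together, but the GEE names no treatment-group cluster, so precision is overstated if outcomes correlate within groups

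*Combined protocol and SAP*

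**What the plan says.** Procedures describes the allocation in two ways. Its opening reads as individual randomisation, "OB smokers (n=60) will be randomized to either a combined self-regulation plus large changes (SR) intervention", with 30 per arm. Later in the same paragraph the mechanism is given: "The study will include up to 18 groups each run in succession with approximately 4-6 participants recruited for each group", of whom 3–5 are expected to start, and then "Groups will be randomly assigned to one of the two treatment conditions using a random number generator after participants have completed all pretreatment assessments". That later sentence makes the treatment group the unit of assignment.

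The Interventions text in the same section has each group treated as a unit: "The treatment will consist of 16 weekly, 60-minute, group sessions that will take place remotely using Zoom".

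The outcome model in the Data Analysis Plan is one sentence: "Generalized estimating equations (GEE) Group x Time analyses will be used for weight change and abstinence". Both outcomes are then to be analysed by time and condition, so the word Group there reads as trial arm, not treatment group. Abstinence enters at four visits from Quit Day onward; weight enters at those four and at baseline. No cluster variable, working correlation, variance estimator or allowance for few clusters is named. The mechanism analysis proceeds by "using regression analyses to test the effects of treatment on proposed mechanistic variables at week 9, controlling for baseline values", again without reference to the treatment group. The section ends: "Notably, detection of statistically significant effects is not an objective in this limited-powered study".

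**The concern.** Members of a treatment group share an allocation, an interventionist and 16 weeks of sessions, so their outcomes may be correlated. The independent units for comparing the arms are then the 12–18 groups, not the 60 people. A GEE clustered on participant handles the repeated visits but treats people in the same group as independent.

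The two outcomes are not equally exposed. Abstinence has no baseline value in the model, so any shared group effect goes straight into the arm contrast at each visit. For weight, a group effect that is constant over time cancels from the change since baseline; the problem arises only if members' weight changes are correlated, which is plausible when they attend the same sessions.

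What is at stake is stated precision. Specific Aims lists preliminary effect sizes among the products, alongside feasibility and acceptability, and Project Purpose says the data are to inform a larger trial. Intervals that look tighter than the design supports would mislead that planning.

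**Working it through.** **No figure to reproduce.** The sample size of 60 is given without power, SD, event rates or ICC. It fits the group plan: 18 groups of 3–5 hold 54–90 people.

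**Inputs.** N = 60, up to 18 groups and 3–5 starters per group (Procedures). This gives 60/18 = 3.33 per group with 18 groups, 60/4 = 15 groups, or 60/5 = 12 groups. The ICC is not in the documents; 0.01, 0.05 and 0.10 are assumed.

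**Step 1: standard error and interval width.** Design effect DE = 1 + (m − 1) × ICC, where m is group size. The correct SE is √DE times the participant-level SE. With G groups, the interval ratio against a z-based interval is t(0.975, G − 2) × √DE / 1.96. Each cell shows DE, SE increase, interval ratio.

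| Groups × size | ICC 0.01 | ICC 0.05 | ICC 0.10 |
|---|---|---|---|
| 18 × 3.33 | 1.023, +1.2%, 1.09 | 1.117, +5.7%, 1.14 | 1.233, +11.1%, 1.20 |
| 15 × 4 | 1.030, +1.5%, 1.12 | 1.150, +7.2%, 1.18 | 1.300, +14.0%, 1.26 |
| 12 × 5 | 1.040, +2.0%, 1.16 | 1.200, +9.5%, 1.25 | 1.400, +18.3%, 1.35 |

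The interval ratio has two parts. For 15 groups, t on 13 df is 2.160, and 2.160/1.96 = 1.10, which applies even at ICC 0; only √DE is due to clustering. Against t on 58 df the intervals for 15 groups of 4 are 10%, 16% and 23% wider. Effective sample size, 60/DE, is 58.3, 52.2 and 46.2.

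**Step 2: coverage of a participant-level 95% interval.** Simulated with no true effect and 15 groups of 4 (8 versus 7): 40,000 runs for weight change; 20,000 for abstinence, with four visits, 30% abstinent and latent participant correlation 0.4.

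| Outcome | ICC 0 | ICC 0.05 | ICC 0.10 |
|---|---|---|---|
| Weight change, changes correlated within group | 94.0% | 92.0% | 90.2% |
| 3-month abstinence (latent ICC) | 94.0% | 92.8% | 91.8% |

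When the group effect on weight is constant over time, coverage stays at about 94.2%, so nothing is lost. Coverage is already 94.0% at ICC 0 because of the small sample. Clustering itself therefore costs 2.0 and 3.8 points for weight change, and 1.2 and 2.2 points for abstinence.

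**Step 3: the ICC scale for abstinence.** The percentages in step 1 use an ICC on the observed scale. At 30% abstinence, latent 0.05 and 0.10 correspond to about 0.029 and 0.058 observed. With groups of 4, √(1 + 3 × 0.029) = 1.04 and √(1 + 3 × 0.058) = 1.08, so the SE increase is about 4% and 8%, not 7% and 14%.

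**Step 4: is naming the cluster enough?** No. With 12 groups of 5, 15 groups of 3–5 and 18 groups of 3–4 (30,000 runs each), a group-level sandwich with z covers only 89–92%. Kauermann-Carroll standard errors with t on G − 2 df give 95% at every ICC tried; Mancl-DeRouen with the same t gives 96–97%.

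**The case against.** The strongest reply is that this is a pilot that disclaims significance testing, does not promise confidence intervals, and will report point estimates that clustering does not bias. No decision in the plan would change. This stands, and it limits the harm to precision. But an effect size handed to the planners of a larger trial needs an honest statement of uncertainty, and a GEE produces standard errors whether or not a test is the aim.

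Second, the size rests on two unknowns: participant-level clustering is inferred from the plan's silence, and there is no ICC. At ICC 0.01 the SE is only 1–2% too small, and weight may lose nothing. This also stands, so the conclusion must stay conditional. The silence is nevertheless what needs repair, because even an analyst who chose the treatment group as cluster would under-cover without a correction.

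Third, the simulations have no missing data, whereas the plan imputes missing participants as smoking and as regaining 0.3 kg/month, which also affects stated precision. The coverage figures are therefore illustrative, not predictions for this trial.

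Fourth, other analyses would respect the design, including Mancl-DeRouen standard errors or a group-level summary or permutation analysis. That is fair: the requirement is to respect the groups and allow for their small number, and the wording proposed below is one sound way.

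**Conclusion.** The concern holds. The plan assigns and treats whole groups, but neither the GEE nor the mechanism regressions mention them. If the GEE is clustered on participant and outcomes correlate within groups, stated precision is too high: across 12–18 groups the correct SE is 1–2% larger at an observed-scale ICC of 0.01, 6–10% at 0.05 and 11–18% at 0.10. For abstinence, a latent ICC of 0.05 or 0.10 corresponds to about 4% or 8% with groups of 4. For weight, the loss depends on correlated changes, not merely on groups that differ by a constant amount. Point estimates and the sample size are unaffected. This should be fixed before analysis because the remedy is cheap, but it does not invalidate the trial.

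**What to change.** In the Data Analysis Plan, after the GEE sentence, add:

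> The treatment group is the GEE cluster, with independence working correlation, Kauermann-Carroll bias-corrected standard errors and a t reference on (number of treatment groups − 2) degrees of freedom. The mechanism regressions use the same cluster and correction.

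If a mixed model is preferred for weight, it needs group-by-time random effects and small-sample degrees of freedom; a group random intercept alone would not capture correlated changes.

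Report the ICC with its interval as descriptive only. At ICC 0.05 with 15 groups of 4 its SE is √[2 × 0.95² × 1.15² / (4 × 3 × 14)] = 0.12, too large to plan from.

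In Procedures, reconcile the wording that randomises smokers with the wording that randomises groups.

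**Cost:** wording and a treatment-group identifier in the data set, with no new data. Point estimates in the main condition-by-time model do not change, since the main analysis imputes every missing value and the data are balanced. The downside is wider intervals, about 10% wider than z-based ones with 15 groups even if the true ICC is 0.

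**A separate, secondary point:** no blocking is stated. If simple randomisation is meant, the chance that one arm gets at least two thirds of the groups is 39%, 30% or 24% with 12, 15 or 18 groups (binomial, probability 0.5). Concealed permuted blocks of groups would better deliver the intended 30 per arm.
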